## **1. Abstract**

In order to improve the results of ECMO and septic patients, various techniques used to reduce the systemic inflammatory response syndrome, immunocorrection, and others. Today, there are many ways to prevent the development of a systemic inflammatory response by removing leukocytes from the bloodstream by inserting a filter with a special screen into the perfusion circuit to remove leukocytes and prevent them from entering the systemic circulation.

The most effective method is the hemoabsorption, intended for additional therapy of patients with elevated levels of cytokines in the context of systemic inflammatory response syndrome. In-patient with acute respiratory distress syndrome and cardiogenic septic shock on the background of extracorporeal membrane oxygenation (ECMO) and mechanical support of the left ventricle, additionally installed a system for veno-venous hemofiltration, a system designed to eliminate a wide range of inflammatory mediators also various proteins and metabolites.

New methods developed to restore the function of affected organs after implantation of mechanical support devices and patients with sepsis will be a great importance both for Kazakhstan and for countries with similar category of patients, which will improve the efficiency of surgical treatment and reduce the level of complications and mortality.

Clinical research data will form the basis of practical protocols for extracorporeal membrane oxygenation (ECMO) and patients with sepsis, which will improve organ repair, reduce postoperative complications, improve quality of life and reduce mortality after surgery.

The goal of the program: Improvement of organ-substituting technologies in the treatment of heart and respiratory failure.

## **Study Design**

Study Type: Interventional (Clinical Trial)

Estimated Enrollment: 90 Participants

Allocation: randomized

Interventional Model: Parallel assignment

Masking: None (Open Label)

The results of a clinical study will improve the effectiveness of surgical treatment and reduce the level of complications and mortality, improve the quality of life of patients undergoing cardiac surgery. The introduction of a clinical protocol for the use of an extracorporeal adsorbent in this category of patients will allow standardizing this technique in the Republic of Kazakhstan.

The data obtained on the treatment of patients with heart and lung failure and organ restoration through the use of innovative technologies will provide the necessary information to

improve the quality of tertiary care and the quality of life of patients in Kazakhstan and around the world. The developed methods can be used as new standards and recommendations both domestically and abroad through successful presentations at various conferences. If there are unique developments in the use of an extracorporeal adsorbent, patent applications will be filed.

In general, the expected effectiveness and efficiency of the proposed project will make a significant contribution to the development of transplantation, cardiac surgery and cardiology in Kazakhstan.

## **2. Explanatory note**

### **1. General information**

1.1. The title of the scientific and technical program (hereinafter - the program): "Innovative solutions to organ-substituting technologies in the treatment of heart and pulmonary failure".

1.2. The name of the priority area for the development of science, according to which the application is submitted. The Science of Life and health.

1.3. Name of the specialized scientific field in which the application is submitted, type of research. Biotechnologies in medicine: New technologies and biologically active substances for solving anti, postnatal development aging, prolonging of human life problems.

1.4. Estimated project start date and duration. 2021-2023 years.

1.5 Requested amount of grant funding for the entire duration of the project for 2021 - 2023 – 63 083 thousand tenge, 2021 – 18 574 thousand tenge, 2022- 22 228 thousand tenge, 2023 – 22 280 thousand tenge.

1.6. Keywords that characterize the industry and the direction of the application for the selection of experts. Organ-substituting technologies. Heart failure. Pulmonary failure. Sepsis. Extracorporeal membrane oxygenation. Adsorber

## **2. General project concept**

### **2.1. Introduction**

Principal Investigator – [name], Chief of Cardiac Surgery Department of JSC "National Research Center for Cardiac Surgery" (hereinafter referred to as JSC NNCS).

JSC "National Research Center for Cardiac Surgery" is a research center that implements a program for treating patients with chronic heart failure (CHF) and pulmonary failure (PF) at the terminal stage, including orthotopic transplantation of the heart and lungs, mechanical support of the blood circulation.

The implementation of this project will improve the effectiveness of surgical treatment and reduce the level of complications and mortality among patients with heart failure and heart failure in the terminal stage.

## 2.2. The goal of the program.

Improvement of organ-substituting technologies in the treatment of heart and respiratory failure.

## 2.3. Objectives of the program.

**Objective 1. To study the restoration of organ function during implantation of extracorporeal membrane oxygenation (ECMO), as an organ replacement, in cardiac and / or respiratory failure.**

**Subtask 1.1.** Evaluation of the recovery of organ function during ECMO using extracorporeal hemocorrection procedure.

**Subtask 1.2.** Evaluation of the normalization of the organism immune response and restoration of organ function when conducting ECMO using the extracorporeal cytokine adsorber.

**Subtask 1.3.** Evaluation of the normalization of the organism immune response and restoration of organ function when conducting ECMO using the extracorporeal hemoperfusion cartridge.

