## 3. Scientific novelty and significance of the program

According to statistics, CHF is an increasingly widespread condition in most countries of the world. In the general population within adults, CHF is revealed annually in 1-2% of the population [1]. With increasing age, the incidence of CHF is increasing exponentially. The incidence of CHF reveals its multiple increase in each subsequent age group: in 25-34 years old - 0.02 per 1000 population, in 55-64 - 3.0-4.0 per 1000, 75-84 years - 13.0- 14.0 per 1000 population [2-5]. The constant increase in the number of patients with CHF is associated with both an increase in the life expectancy of patients and a decrease in mortality among patients with a complicated course of acute myocardial infarction, heart defects, etc. The most common causes of CHF are arterial

hypertension, coronary heart disease and myocardial infarction. The gold standard for treating patients with terminal heart failure, tolerance to drug therapy is heart transplantation.

In 2012 the JSC “National Research Center for Cardiac Surgery” developed the heart transplantation program in Kazakhstan. Considering the geographical features of our country (donor hearts are transported from regions remote from the Center > 1000 km.), remote delivery and heart preservation has been developed using an organ preservation system. The Center has been performed 81 heart transplants for 8 years. The survival rate by 12 months was 80%. According to data, for 2018, more than 200 people need heart transplants every year in Kazakhstan.

The lack of donor organs remains the most important factor hindering the development of lung and heart transplants throughout the world and in our country.

Extracorporeal membrane oxygenation (ECMO) is a procedure for prolonged cardiopulmonary bypass and oxygenation of the blood outside the body, used in patients with acutely frisky and potentially reversible respiratory and / or heart failure, whose treatment is not amenable to the maximum standard therapy. In 2011, the JSC “National Research Center for Cardiac Surgery” launched a program to provide ECMO in Kazakhstan, and in 2016 the Center entered to the World Register ELSO (Extracorporeal Life Support Organization) [6-14].

Sepsis, septic shock and SIRS are life-threatening conditions associated with an overreacting immune response. The deregulated response can lead to multiple organ dysfunction [15-21].

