#### **4. Research methods and ethical issues**

Patients before implantation of ECMO and/or patients with sepsis will be enrolled in the study after giving a written, signed informed consent.

The participants will be randomized into 3 groups:

- **Intervention group #1** a cytokine adsorber will be used (30 patients): patients on ECMO – subgroup A; septic patients – subgroup B.
- **Intervention group #2** an extracorporeal hemoperfusion cartridge will be used (30 patients): patients on ECMO – subgroup C, septic patients – subgroup D.

- **Control group #3** without using extracorporeal adsorber (30 patients): patients on ECMO subgroup - E, septic patients - subgroup F.

The investigators will collect demographic, clinical and laboratory data about patients before, during and after the operation

The incidence of early cellular or humoral rejection, length of ventilation, ICU and hospital stay, the use of vasopressors and inotropes in the perioperative period and incidence of perioperative complications and survival will be documented.

The level of cytokines (IL-1, IL-6, IL-8, IL-10, tumor necrosis factor-alfa) and complements before, during and after the use of ECMO, patients with sepsis will be determined if the investigators find relevant difference between the two groups in clinical variables.

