#### Secondary outcomes

1. Ventilator free days (VFD) [Time Frame: 30 days]

Ventilator free days (VFD) in the first 30 days after randomization, where invasive mechanical ventilation (IMV), non-invasive ventilation (NIV) and ECMO are defined as ventilator days. VFD=0, if the patient dies in the first 30 days after randomization

2. Time to extubation from ventilation and explantation from ECMO [ Time Frame: 30 days ]

Time to extubation from ventilation and explantation from ECMO. Death under ventilation and/or ECMO will be analyzed as a competing event. The time will be censored at the time of last visit for surviving patients under ventilation and/or ECMO.

3. Difference of d-dimers [Time Frame: 24, 48, 72 hours]

Comparison to enrollment or between 3 groups at 24, 48, 72 h

4. Difference of Serum lactate [Time Frame: 24, 48, 72 hours]

Comparison to enrollment or between 3 groups at 24, 48, 72 h

5. SOFA-Score [Time Frame: 24, 48, 72 hours]

Sequential Organ Failure Assessment Score at 24, 48, 72 h (values from 6 to 24, where the higher values explain higher disease severity)

6. Serious adverse device effects [Time Frame: 30 days]

Serious complications or malfunctions related to the CytoSorb device

7. Adverse event of special interest: air in the ECMO system [Time Frame: 30 days]

- Unintended air in the ECMO system during operation of the device
- 8. Adverse event of special interest: blood-clotting in the ECMO system [Time Frame: 30 days]
  - Unintended blood-clotting in the ECMO system during operation of the device
- 9. Adverse event of special interest: bleeding complications [Time Frame: 30 days]
  - Major bleeding events

*Patient with septic shock*

- 1. Difference of Cytokine response [ Time Frame: 24-48 hours of septic shock ]
  - Cytokine response: Level of procalcitonin, Level of C-reactive protein, Level of interleukin-1, Level of interleukin-6, Level of interleukin-8, Level of interleukin-10, Level of Tumor Necrosis Factor-  $\alpha$  at 24, 48 hours.

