### Statistical studies

1) Statistical data processing

2) Comparison and analysis of source data

After data receiving, statistical analysis will be performed using SPSS Statistics software version 22. For quantitative data, the Mann-Whitney Yu non-parametric test and parametric t-test will be performed, and Fisher's non-parametric exact test and  $\chi^2$  parametric test will be performed for qualitative studies. Also, a logistic regression for categorical outcomes and a survival analysis (non-parametric Kaplan-Meier and parametric Cox regression) will be performed.

**Ages:**18 Years and older

**Sex:** All

**Accepts healthy volunteers:** No

Groups	Inclusion criteria	Exclusion Criteria:
ICU patients with ECMO	

• Hemodynamic support with vasopressors

• Procalcitonin level <math>\geq 1</math> ng/ml

• Invasive hemodynamic monitoring

• Written informed content

	

• age <math>< 18</math> years

• acute liver or kidney failure straight before transplantation

• the patient declines participating in the study

ICU patients with septic shock of medical origin	

• Signs of hypoperfusion: serum lactate <math>>2</math> mmol/L, low central venous oxygen saturation (ScvO2) (<math><70\%</math>) or high ScvO2 (<math>>85\%</math>), metabolic acidosis, oligo-anuria,

	

• Patients under 18 years

• Pregnancy (bHCG test positivity)

• Surgical intervention in context with the septic insult

	
high venous-to-arterial CO2-gap (dCO2 >6 mm Hg)
 
 
• Hemodynamic support with vasopressors
 
• Procalcitonin level <math>\geq</math> 1 ng/ml
 
• Invasive hemodynamic monitoring
 
• Written informed content
 
	
New York Heart Association IV heart failure
 
 
• Acute coronary syndrome
 
• Acute haematological malignancies
 
• Immunosuppression, systemic steroid therapy (>10mg prednisolon/day)
 
• Human immunodeficiency virus infection (HIV) and active AIDS
 
• Patients with donated organs
 
• Thrombocytopenia (<20.000/ml)
 
• More than 10%-of body surface area with third degree burn
 

--	---	--

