## 6. Project implementation plan

№ i/n	Name of task, activities for implementation of project tasks	Duration (in months)	Start and end date of work * (dd / mm / yy).	Years of project implementation, expected project results (in terms of tasks and activities)		
				2021	2021	2022
1.	Literature review on treatment of patients with failure of heart and lung within innovation technolog	6 months	01.01.2021-01.06.2021			
1.1	Literature review of patients on ECMO with using extracorporeal cytokine adsorber or hemoperfusion cartridge			Literature review for ECMO patients using an extracorporeal cytokine adsorber and an extracorporeal		

				hemoperfusion cartridge. Obtaining the results of the literary review.		
1.2	Literature review of septic patients with using extracorporeal cytokine adsorber or hemoperfusion cartridge			Literature review for septic patients using an extracorporeal cytokine adsorber and an extracorporeal hemoperfusion cartridge will be conducted. Obtaining the results of the literary review.		
2.	Recruiting patients on ECMO / septic patients with using extracorporeal cytokine adsorber or hemoperfusion cartridge depend of diagnosis	36 months	01.01.2021-31.12.2023	Initial patient condition will be studied	Initial patient condition will be studied	Initial patient condition will be studied
2.1	Examination of patients, verification of diagnosis and other procedure					
2.2	Study of directly clinical results of after using extracorporeal adsorbent on ECMO patients					
2.3	Study of directly clinical results of after using extracorporeal adsorbent on patients with sepsis.					
3.	Clinical and laboratory data will be analyzed on basis of clinical research	12 months	01.01.2023-31.12.2023			A protocol will be developed and optimized for the implementation of

						extracorporeal adsorber technologies for this category of patients
3.1	A protocol for optimization of introduction novel technology will be developed and implemented					
3.2.	Protocol implementation					
4.	Preparation of publications, reports, development of methodological guidelines	24 months	2022-2023		Article in international and local journals	Article in international and local journals
5.	Creation of intermediate and final reports	annually	2021-2023	Interim and final reports will be generated	Interim and final reports will be generated.	Interim and final reports will be generated.

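### The ECMO cohort mixes cardiac and respiratory indications, and the tests named for quantitative outcomes cannot use the indication; where it is prognostic, this gives away precision at 15 patients per arm.

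*Combined protocol and SAP*

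**What the plan says.** Section 2.3, Objective 1, sets one objective for ECMO "as an organ replacement, in cardiac and / or respiratory failure". Section 3 describes ECMO the same way, for "potentially reversible respiratory and / or heart failure". In the eligibility table under Statistical studies, the row "ICU patients with ECMO" asks for vasopressor support, a procalcitonin threshold, invasive monitoring and consent. It neither restricts the indication nor asks for it to be recorded.

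On allocation, section 4 says "The participants will be randomized into 3 groups". The only division within an arm is by cohort, for example "patients on ECMO – subgroup A; septic patients – subgroup B". The Study Design table puts 15 patients in each of the six cells. No stratification or blocking factor is named.

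For quantitative data, Statistical studies says "the Mann-Whitney Yu non-parametric test and parametric t-test will be performed". Fisher's exact and chi-square tests, logistic regression, Kaplan-Meier and Cox regression are also named, none with a covariate. The ECMO primary outcome is a set of cytokine levels, so it falls to the two unadjusted tests. So do ventilator-free days, where "invasive mechanical ventilation (IMV), non-invasive ventilation (NIV) and ECMO are defined as ventilator days".

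**The concern.** The outcome definitions link some results to the indication. ECMO days count against ventilator-free days, and secondary outcome 2 needs both extubation and explantation. The time on the clock therefore depends on which organ has to recover. A cardiac patient's clock can run until the circulation manages without ECMO, and a respiratory patient's until the lungs do.

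Indication is fixed before treatment. If it predicts an outcome and the analysis ignores it, the difference between indications is counted as noise. With 15 per arm there is little precision to spare. An ECMO-versus-sepsis stratum would not help, because the mixture lies inside the ECMO cohort.

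**Working it through.** **Inputs from the plan.** 3 × 30 = 90 and 6 × 15 = 90, so the stated enrolment agrees with the table; the ECMO cohort is 3 × 15 = 45. No alpha, power, effect size or SD is given, so there is no sample-size calculation to reproduce.

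**Assumptions.** Two-sided 5% test; 15 v 15; true device effect of 1 SD; a share p of ECMO patients with one indication; outcome shift D between indications, in within-indication SDs. The documents give neither p nor D, so both are varied.

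**Benchmark.** The standard error of a difference is √(2/15) = 0.365 SD. The difference detectable with 80% power is (1.960 + 0.842) × 0.365 = 1.02 SD (1.06 SD by the t distribution).

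**Chance imbalance.** With independent binomial(15, p) counts, the probability of a gap of 4 or more patients of one indication (4/15 = 27 percentage points) is:

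| p | two given arms | some pair of the three |
|---|---|---|
| 0.5 | 20% | 41% |
| 0.3 | 16% | 34% |
| 0.2 | 11% | 24% |

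If exactly 15 of the 30 patients in two arms had one indication, the two-arm figure would be 14%. A gap of 4 moves the unadjusted difference by 0.27 × D SD, which at D = 1 is 0.27/0.365 = 0.73 standard errors.

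**Extra variance.** Ignoring the indication multiplies the variance by V = 1 + p(1−p)D². The variance of the difference becomes 2/15 + 2p(1−p)D²/15. The second term is exactly the variance of the shift caused by chance imbalance, so imbalance and extra variance are one problem and must not be counted twice.

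**Power.** Unadjusted: noncentrality 1/(√V × 0.365), 28 df. For p = 0.5 and D = 1, V = 1.25 and the noncentrality is 1/(1.118 × 0.365) = 2.45, giving 65.7%. Adjusted without blocking: 27 df and variance × (1 + 1/26), giving 73.6% whatever D is. Adjusted with allocation blocked by indication: 75.2%.

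| mix | D | V | information lost, 1 − 1/V | t-test | adjusted |
|---|---|---|---|---|---|
| any | 0 | 1.00 | 0% | 75% | 74–75% |
| 50:50 | 0.5 | 1.06 | 6% | 73% | 74–75% |
| 80:20 | 1.0 | 1.16 | 14% | 69% | 74–75% |
| 50:50 | 1.0 | 1.25 | 20% | 66% | 74–75% |
| 50:50 | 1.5 | 1.56 | 36% | 56% | 74–75% |

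Simulation of the last four rows gives 73% v 74%, 67% v 73%, 66% v 75% and 55% v 73%, within about two points of the formula. Mann-Whitney at 50:50 gives 62% (D = 1) and 50% (D = 1.5).

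**Type I error.** Simulated with no device effect over a range of mixes and shifts, the t-test rejected in 4.6–5.6% of trials and Mann-Whitney in 4.3–5.0%. Both keep their level.

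**The case against.** The strongest reply is that the gain may be small. The documents give no evidence that cytokines, D-dimer, lactate or SOFA differ by indication, and the mechanism above is argued only for two secondary outcomes. The mix may be uneven: this is a cardiac surgery centre and ECMO entry requires vasopressors. At a shift of 0.5 SD the gain is 0–2 points. Logistic and Cox regression are already named and could carry the indication. A pre-ECMO cytokine level is collected and might absorb some of the difference. The larger limit is 15 per arm, which adjustment does not remove.

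Most of this stands as a limit on size. It does not answer the point. No covariate is named for the regression models, and neither the t-test nor Mann-Whitney can use the indication or a baseline value as a covariate.

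A reader might infer that every ECMO comparison is blurred. The documents do not support that, because the loss depends on an unstated shift and mix and vanishes when either is negligible. A reader might also infer that a chance surplus of one indication biases the device comparison. Given a particular imbalance, the false-positive rate does rise: at 9 v 5, simulation gives 5.9%, 7.2% and 8.7% for shifts of 0.5, 1 and 1.5 SD. Over all allocations it stays near 5%, so this is the same extra variance seen from another side.

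**Conclusion.** The point holds as a matter of precision. The plan pools two indications, does not use the indication in allocation, and names tests for quantitative outcomes that cannot use it. Ventilator-free days and time to extubation and explantation are the outcomes most plausibly affected. For the primary cytokine outcome the omission is certain, but its effect is unknown.

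For a 1 SD device effect the gain in power from adjustment runs from about 0–2 points (0.5 SD shift), through about 5–6 points (80:20 mix, 1 SD) and 8–9 points (even mix, 1 SD), to about 18 points (even mix, 1.5 SD). With no shift, adjustment loses about 1–2 points. These figures rest on assumed values of p, D, alpha and device effect. The choice is lopsided enough to favour adjustment, as an inexpensive improvement and not as the cure for a small trial.

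**What to change.** In Statistical studies, state that the ECMO indication (cardiac or respiratory) is recorded at enrolment. The investigators should define the class for combined failure before outcomes are compared. Then:

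- Quantitative ECMO outcomes: use the indication as a covariate in a linear model on the log or rank scale, or as the stratum of a van Elteren test. The rank-based options suit ventilator-free days, where deaths share the value zero.
- Logistic and Cox models already named: use it as a covariate or stratum.
- Rare device events: leave them unadjusted, as the cells would be too small.
- Where ECMO patients remain to be allocated, block the list by indication if feasible.

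The cost is one baseline field and one model parameter among 45 ECMO patients, with no change to sample size or endpoints. Section 6, row 2.1, already provides for "Examination of patients, verification of diagnosis and other procedure". That should make the indication easy to obtain, but the row does not say that it is recorded, so the field has to be added explicitly. Because the trial is open label, fixing the factor before outcomes are compared also prevents its being chosen after the results are seen.
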